12.2 A Guide to Interpreting the Causality Question

When making an assessment of causality consider the following factors when deciding if there

is a 'reasonable possibility' that an AE may have been caused by the drug.

- Time Course. Exposure to suspect drug. Has the patient actually received the suspect drug? Did the AE occur in a reasonable temporal relationship to the administration of the suspect drug?
- Consistency with known drug profile. Was the AE consistent with the previous knowledge of the suspect drug (pharmacology and toxicology) or drugs of the same pharmacological class? Or could the AE be anticipated from its pharmacological properties?
- De-challenge experience. Did the AE resolve or improve on stopping or reducing the dose of the suspect drug?
- No alternative cause. The AE cannot be reasonably explained by another aetiology such as the underlying disease, other drugs, other host or environmental factors.
- Re-challenge experience. Did the AE reoccur if the suspected drug was reintroduced after having been stopped? AstraZeneca would not normally recommend or support a re-challenge.
- Laboratory tests. A specific laboratory investigation (if performed) has confirmed the relationship.

In difficult cases, other factors could be considered such as:

- Is this a recognized feature of overdose of the drug?
- Is there a known mechanism?

Causality of 'related' is made if following a review of the relevant data, there is evidence for a 'reasonable possibility' of a causal relationship for the individual case. The expression 'reasonable possibility' of a causal relationship is meant to convey, in general, that there are facts (evidence) or arguments to suggest a causal relationship.

The causality assessment is performed based on the available data including enough information to make an informed judgment. With limited or insufficient information in the case, it is likely that the event(s) will be assessed as 'not related'.

Causal relationship in cases where the disease under study has deteriorated due to lack of effect should be classified as no reasonable possibility.

13. APPENDIX B INTERNATIONAL AIRLINE TRANSPORTATION ASSOCIATION (IATA) 6.2 GUIDANCE DOCUMENT

13.1 Labelling and Shipment of Biohazard Samples

International Airline Transportation Association (IATA) classifies biohazardous agents into 3 categories. For transport purposes the classification of infectious substances according to risk groups was removed from the Dangerous Goods Regulations (DGR) in the 46th edition (2005). Infectious substances are now classified either as Category A, Category B or Exempt. There is no direct relationship between Risk Groups and categories A and B.

Category A Infectious Substances are infectious substances in a form that, when exposure to it occurs, is capable of causing permanent disability, life-threatening or fatal disease in otherwise healthy humans or animals. Category A pathogens are eg, Ebola, Lassa fever virus:

- Are to be packed and shipped in accordance with IATA Instruction 602.

Category B Infectious Substances are infectious Substances that do not meet the criteria for inclusion in Category A. Category B pathogens are eg, Hepatitis A, B, C, D, and E viruses, Human immunodeficiency virus (HIV) types 1 and 2. They are assigned the following UN number and proper shipping name:

- UN 3373 – Biological Substance, Category B
- are to be packed in accordance with UN3373 and IATA 650

Exempt - all other materials with minimal risk of containing pathogens

- Clinical trial samples will fall into Category B or exempt under IATA regulations
- Clinical trial samples will routinely be packed and transported at ambient temperature in IATA 650 compliant packaging
- **Biological samples transported in dry ice require additional dangerous goods specification for the dry-ice content**
- IATA compliant courier and packaging materials should be used for packing and transportation and packing should be done by an IATA certified person, as applicable

- Samples routinely transported by road or rail are subject to local regulations which require that they are also packed and transported in a safe and appropriate way to contain any risk of infection or contamination by using approved couriers and packaging / containment materials at all times. The IATA 650 biological sample containment standards are encouraged wherever possible when road or rail transport is used.

14. APPENDIX C ALGORITHM ON MANAGEMENT OF SUSTAINED ELEVATED LIVER SAFETY ABNORMALITIES

14.1 Algorithm on Management of Sustained Elevated Liver Safety Abnormalities

The monitoring for liver safety will be performed using the serum levels of AST, ALT and TB (see [Figure 1](#) Sustained elevated liver safety abnormalities flow chart).

Patients with a central laboratory ALT and/or AST >3 X ULN will be scheduled for a follow-up visit within 3 days following receipt of the initial laboratory results, to obtain repeat central laboratory ALT, AST, TB and Alkaline Phosphatase (ALK-P). In the event that the repeat laboratory assessments cannot be obtained within 3 days, the Investigator is encouraged to discuss possible alternatives with the Sponsor. Patients should remain on study medication until confirmatory results are obtained, unless otherwise contraindicated.

- **If the repeat ALT and AST are $\leq 3X$ ULN**, patient should continue study treatment according to their original visit schedule unless otherwise contraindicated.
- **If the repeat ALT and/or AST are $>3X$ ULN but $\leq 8X$ ULN and $TB \leq 2X$ ULN**, the patient's medical history, including details of risk factors for liver diseases, should be evaluated for potential underlying aetiologies. In addition, specialized blood sampling will be performed to evaluate liver function as well as identify potential causes of laboratory elevation(s). The Investigator should continue to monitor the patient's liver tests every 3 days following receipt of the prior laboratory results until the ALT and AST are $\leq 2X$ ULN or until ALT and AST are at or below baseline levels. The frequency of retesting can decrease to once a week or less if abnormalities stabilize and the patient is asymptomatic. Patients should remain on study medication unless confirmatory results indicate that a criterion for discontinuation has been met or continuing study medication would be otherwise contraindicated.

14.2 Patients must be Discontinued from the Study if an Initial and Repeat Confirmatory Laboratory Tests Meet any of the Following Criteria:

- ALT and/or AST are > 3 x ULN and $TB > 2$ x ULN

- ALT and/or AST are >5 x ULN for > 14 consecutive days, at any time after initial confirmatory results
- ALT and/or AST are >8 x ULN

In each of these situations, study medication will be discontinued, the Sponsor notified and the End of Treatment Visit performed within 3 days of the confirmed laboratory results (see Section 3.10 in the CSP).

At the End of Treatment Visit, medical history including details of risk factors for liver diseases (if not previously assessed) will be requested and additional blood sampling performed (Specialized Liver Panel and Liver Discontinuation Panel, see detailed below). Patient should also be scheduled for a Follow-up Visit (ie, procedures of Visit 10) 3 weeks after discontinuation of investigational product. A referral consultation to a hepatologist or gastroenterologist (specializing in liver abnormalities) should be obtained.

Any additional tests and/or examinations should be carried out at the discretion of the Investigator. Any further investigations and laboratory results for patients with abnormal laboratory values at the Follow-up Visit should be made available to the Sponsor upon request.

Additional information, including but not limited to completion of supplemental eCRFs may be requested for certain adverse events and/or laboratory abnormalities which are reported/identified as part of the hepatic safety surveillance.

Following the End of Treatment Visit, the Investigator should continue to monitor the patient's liver tests every 3 days following receipt of the prior laboratory results until the ALT and AST are ≤ 2 x ULN or until ALT and AST are at or below baseline levels. The frequency of retesting can decrease to once a week or less if abnormalities stabilize and the patient is asymptomatic.

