3.10 Discontinuation of investigational product

Patients may be discontinued from IP in the following situations:

- Patient decision. The patient may, at any time, discontinue study treatment, without prejudice to further treatment. Patients who choose to discontinue study treatment are expected to continue in the study until the closing of the study.
- Safety reasons as judged by the Investigator, by or an AZ representative.
- Severe non-compliance to protocol as judged by the investigator and/or AZ

Subjects MUST discontinue study treatment (investigational or non-investigational treatment) for any of the following reasons:

- Any clinical AE, laboratory abnormality or inter current illness which, in the opinion of the Investigator, indicates that continued participation in the study is not in the best interest of the subject.
- Pregnancy
- Termination of the study by AstraZeneca.
- Loss of ability to freely provide consent through imprisonment or involuntarily incarceration for treatment of either a psychiatric or physical (e.g., infectious disease) illness.
- Protocol-defined major hypoglycemia episodes.
- Liver criteria:

ALT and/or AST >3 times the upper limit of normal (ULN) and concomitant TB >2 times ULN confirmed at a repeated measurement at the central laboratory (which should be obtained within 3 days, whenever possible, following receipt of the initial laboratory results)

ALT and/or AST >8 times ULN confirmed at a repeated measurement at the central laboratory (which should be obtained within 3 days, whenever possible, following receipt of the initial laboratory results)

ALT and/or AST >5 times ULN confirmed at the central laboratory and sustained over a period of 14 days or more

(See Appendix D Algorithm on Management of Sustained Elevated Liver Safety Abnormalities for further details)

- Acute renal insufficiency or worsened chronic renal insufficiency based on sustained ≥ 1.5 times increase in baseline s-creatinine (see page 56 Discontinuation Guidelines due to Acute Kidney Injury).

Clinical indications for discontinuation because of hypoglycemia may include the following:

- Multiple occasions of episodes outlined below that, in the opinion of the Investigator, indicate that continued treatment with study therapy is not in the best interest of the patient. This includes, but is not limited to:

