4.2 Assessments schedule

Table 2 Study Planning and details procedure

Study period	Screening Period	Lead-in period	Randomization		Treatment period			Follow-up period		For details see Protocol Section
	1 ^a Non-fasting	2 ^{b,c} Fasting	3 ^{c,d,e} Fasting	4 ^{c,d,e} Fasting	5 ^{c,d,e} Fasting	6 ^{c,d,e} Fasting	7 ^{c,d,e} Fasting	8 ^{c,d,e} Fasting	9 ^{c,d,e} Fasting	
Visit number	-6	-4	0	1	4	8	12	16	24	27
Week	-6	-4	0	1	4	8	12	16	24	27
Day	-42 to -29	-28	1	8	29	57	85	113	169	190
Visit window	±5	±5	±0	±2	±5	±5	±5	±5	±5	±3

Written informed consent ^f	X										10.4
Demographics	X										4.3
Brief physical examination ^g	X			X	X		X			X	5.2.3
Full physical examination ^h			X						X		5.2.3
Weight and height ⁱ	X		X	X	X	X	X	X	X	X	5.1.4
Medical/surgical history	X										4.3
Inclusion/exclusion criteria	X ^j	X ^k	X ^l								3.1 & 3.2
12-lead ECG ^m		X									5.2.4
Randomisation to study treatment			X								3.4

Study period	Screening Period	Lead-in period	Randomization	Treatment period					Follow-up period	For details see Protocol Section	
	1 ^a Non-fasting	2 ^{b,c} Fasting	3 ^{c,d,e} Fasting	4 ^{c,d,e} Fasting	5 ^{c,d,e} Fasting	6 ^{c,d,e} Fasting	7 ^{c,d,e} Fasting	8 ^{c,d,e} Fasting	9 ^{c,d,e} Fasting		10 ^{c,d} Fasting
Visit number	-6	-4	0	1	4	8	12	16	24	27	
Week											
Day	-42 to -29	-28	1	8	29	57	85	113	169	190	
Visit window		±5	±0	±2	±5	±5	±5	±5	±5	±3	

Blood pressure and Heart Rate	X	X	X	X	X	X	X	X	X	X	5.1.6
Orthostatic blood pressure			X	X	X	X	X	X	X	X	5.2.5.1
Waist Circumference			X						X	X	5.1.7
Concomitant medication	X	X	X	X	X	X	X	X	X	X	7.7
Dietary and life-style advice		X	X	X	X		X	X	X		4.4
Dispense Glucose Meter and Supplies/Provide Instructions		X	X	X	X		X	X	X		5.1.11& 5.2.6.1
Pregnancy test (WOCBP only)	X	X	X	X	X	X	X	X	X	X	5.2.2
Dispensation of Study Medication		X	X				X				7
Drug accountability			X	X	X	X	X	X	X	X	7.6

Study period	Screening Period	Lead-in period	Randomization		Treatment period					Follow-up period	
			3 ^{c,d,e} Fasting	4 ^{c,d,e} Fasting	5 ^{c,d,e} Fasting	6 ^{c,d,e} Fasting	7 ^{c,d,e} Fasting	8 ^{c,d,e} Fasting	9 ^{c,d,e} Fasting	10 ^{c,d} Fasting	For details see Protocol Section
Visit number	1^a Non-fasting	2^{b,c} Fasting	3^{c,d,e} Fasting	4^{c,d,e} Fasting	5^{c,d,e} Fasting	6^{c,d,e} Fasting	7^{c,d,e} Fasting	8^{c,d,e} Fasting	9^{c,d,e} Fasting	10^{c,d} Fasting	
Week	-6	-4	0	1	4	8	12	16	24	27	
Day	-42 to -29	-28	1	8	29	57	85	113	169	190	
Visit window	±5	±5	±0	±2	±5	±5	±5	±5	±5	±3	

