14.5 Liver Discontinuation Panel

For patients who are discontinued from the study as a result of sustained elevated liver safety abnormalities, additional central laboratory tests will be performed at the time of End of Treatment Visit. Similar to the Specialized Liver Panel, these laboratory tests will study the possible causes of the increased ALT and/or AST and/or TB, and may include, but are not limited to, the following tests:

- Cytomegalovirus (CMV) IgM Ab
- Herpes Simplex Virus (HSV) 1 and 2
- Ceruloplasmin
- Toxoplasmosis
- Alpha-1 antitrypsin

For specific details regarding the Specialized Liver Panel or the Liver Discontinuation Panel laboratory tests, refer to the Central Laboratory Manual for this study.

Figure 1 Sustained elevated liver safety abnormalities flow chart

- a In patient with repeat ALT or AST > 3X ULN but ≤ 8X ULN, only patient with TB ≤ 2X ULN at Step 1 should be followed according to Step 2b.
 Patient with an initial TB and confirmatory repeat TB > 2X ULN should be followed according to Step 2d.
- b Please see text above in the Appendix for details on additional assessments to be performed (AE assessment, PE, review of current medical history including focused review to risk factors for liver diseases and collection of blood samples [specialized liver panel or liver discontinuation panel])
- c Confirmatory repeat AST, ALT, ALK-P and TB should be obtained every 3 days following receipt of prior laboratory results, until the ALT and AST are ≤ 2X ULN or until ALT and AST are at or below baseline levels. The frequency of retesting can decrease to once a week or less if abnormalities stabilize and the patient is asymptomatic.

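### Liver retesting may be relaxed with no maximum interval for on-drug patients stable above 5x ULN, so no sample need be due when the mandatory 14-day stop is reached

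*Protocol*

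**What the plan says.** Section 14.1 defines one branch for patients whose repeat ALT or AST is above 3x but not above 8x ULN, with total bilirubin at or below 2x ULN. In that branch:

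- Retesting starts as "liver tests every 3 days following receipt of the prior laboratory results".
- It may then be relaxed: "The frequency of retesting can decrease to once a week or less if abnormalities stabilize and the patient is asymptomatic".
- Drug continues by default: "Patients should remain on study medication unless confirmatory results indicate that a criterion for discontinuation has been met", or unless continuing is otherwise contraindicated.

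Flow chart footnote a, printed after Section 14.5, describes the same enzyme band ("In patient with repeat ALT or AST > 3X ULN but ≤ 8X ULN"). Footnote c repeats the relaxation sentence without exception.

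The duration-based liver stop appears twice. Section 3.10 lists it among the reasons for which treatment must be discontinued: "ALT and/or AST >5 times ULN confirmed at the central laboratory and sustained over a period of 14 days or more". Section 14.2 has "ALT and/or AST are >5 x ULN for > 14 consecutive days, at any time after initial confirmatory results".

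**The concern.** The band from just above 5x to 8x ULN falls under both rules. A stable, asymptomatic value there meets the condition for testing less often. The same stable value, if it lasts, is the mandatory stop. Because drug continues until a result shows that a criterion is met, the stop takes effect only when a sample is taken, and the permitted schedule need not include one at day 14 or 15. A site could follow Section 14.1 to the letter and keep a patient on study drug past a mandatory liver stop.

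**Working it through.** The protocol gives no figure to reproduce, so the check is schedule arithmetic for a patient steady above 5x ULN.

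**Inputs from the protocol.** The stop is reached at 14 days or more (3.10) or at more than 14 days (14.2). The default retest is 3 days after receipt of the prior result. The relaxed retest is weekly or less often, with no upper limit.

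**Assumptions.** The 14-, 21- and 28-day intervals are examples of what the wording allows; the retest rule does not name them. The protocol does not say whether the count starts at the initial or the confirmatory sample, so both are shown. The initial sample is assumed to lie 1 to 6 days before the confirmatory one.

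**Formula.** Let d be the days from the start of the count to the confirmatory sample, and I the retest interval. The stop is first shown on day d + kI, where k is the smallest whole number that brings the sum to the threshold.

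| Interval | From confirmatory sample (d = 0), 3.10 | From confirmatory sample (d = 0), 14.2 | From initial sample (d = 1 to 6), both |
|---|---|---|---|
| 7 days | day 14 | day 21 | days 15 to 20 |
| 14 days | day 14 | day 28 | days 15 to 20 |
| 21 days | day 21 | day 21 | days 22 to 27 |
| 28 days | day 28 | day 28 | days 29 to 34 |

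Examples: weekly, d = 0, under 14.2: 2 x 7 = 14 is not more than 14, so 3 x 7 = 21. Weekly, d = 6: 6 + 7 = 13 is too early, so 6 + 14 = 20.

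**Delay** against the earliest day that meets each wording (day 14 for 3.10, day 15 for 14.2):

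- Weekly: from 14 - 14 = 0 to 21 - 15 = 6 days.
- Every 14 days: from 14 - 14 = 0 to 28 - 15 = 13 days.
- Every 21 days: from 21 - 15 = 6 to 27 - 14 = 13 days.
- Every 28 days: from 28 - 15 = 13 to 34 - 14 = 20 days.

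**Default schedule for comparison.** A strict 3-day interval gives day 15 (5 x 3) with d = 0. Adding an assumed 1 to 3 days for results makes the interval 4, 5 or 6 days, and the first sample falls on day 16, 15 or 18 under both wordings.

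**Relaxation after an initial 3-day phase.** Samples on days 0, 3 and 6 followed by weekly or 14-day tests give day 20; followed by 28-day tests, day 34.

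**Other safeguards.**

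- *Scheduled visits.* Section 4.2 places them on Days 1, 8, 29, 57, 85, 113 and 169. After Day 8 the gaps are 21, 28, 28, 28 and 56 days; with the 5-day windows the last can reach 56 + 5 + 5 = 66 days.
- *Other liver stops.* Enzymes above 8x ULN, or above 3x ULN with bilirubin above 2x ULN, do not catch a patient stable between 5x and 8x ULN with bilirubin at or below 2x ULN.
- *Adjudication.* The triggers named in Section 5.2.6.2 do not name this patient, although that list is not exhaustive.
- *Data monitoring committee.* Section 6.8.2 marks this as not applicable.

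**The case against.** The stop is mandatory and the relaxation is only optional. An optional clause does not override a mandatory one, and an investigator who knows a 14-day count is running would naturally time a sample to it. Section 3.10 also requires discontinuation for any laboratory abnormality that, in the investigator's opinion, makes continuing contrary to the patient's interest. The one frequency that is named, weekly, meets the Section 3.10 wording on day 14 when counted from the confirmatory sample. Part of the weekly delay under Section 14.2 comes from the different wording of the two stops, and the default schedule may itself reach only day 18. The longer intervals are illustrations, and nothing suggests the sponsor intended them above 5x ULN. The flow chart drawing is not shown and could contain a timed step. The group is small: Section 3.2 excludes ALT or AST above 3x ULN at Visit 2, and Section 1.2 reports similar rates of elevated liver tests with dapagliflozin and comparators.

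Most of this stands, and it limits the weight of the point. It does not supply the missing rule. The text permits intervals longer than weekly, the condition that values stabilise is undefined, and no sample is required at day 14 or 15. The one visible flow chart footnote on retest frequency repeats the open-ended wording. A mandatory stop should not depend on the investigator testing more often than the protocol asks.

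**Conclusion.** The concern holds as a minor patient-safety point. For on-drug patients stable above 5x and up to 8x ULN, the written retest rule can miss the day on which the mandatory stop falls due. Exactly weekly testing costs little; the gap lies mainly in longer intervals, and at 28 days it is about two weeks or more under every reading of the count. This rests on a patient who stays above 5x ULN throughout, on illustrative intervals, on an assumed 1 to 6 days between initial and confirmatory samples, and on there being no timed step in the flow chart drawing. No endpoint, analysis, power or alpha figure is affected.

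**What to change.** In Section 14.1, allow the reduced frequency only when both ALT and AST are at or below 5x ULN. Above 5x ULN, either keep the existing 3-day retesting, or allow at most weekly retesting with a fixed sample on day 15 after the first confirmed value above 5x ULN. Day 15 satisfies both the Section 3.10 and the Section 14.2 wording.

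Make the same change in flow chart footnote c where it applies to patients still on study drug. The identical sentence in Section 14.2 about monitoring after the End of Treatment Visit can stay, because study drug has stopped and no stopping count runs there.

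The cost is one qualifying clause, repeated in the footnote if needed, and a few extra chemistry samples in a small number of patients.

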14.3 Guidance on Assessment of Hepatic Laboratory Abnormalities

The following is presented to assist in the evaluation and management of hepatic laboratory values. It is not intended to supplant Investigators' clinical judgment.

Patients who experience ALT and/or AST values >3 x ULN confirmed with a repeated test will have the following performed within 3 days of the confirmed laboratory results:

- AE assessment
- Physical Examination for jaundice and other signs of liver diseases
- Review of relevant risk factors and current history focusing on possible causes of the increased ALT and/or AST and/or TB, including:
 - Use of suspect concomitant medication [including over-the-counter (ie, acetaminophen/paracetamol), herbal and vitamin preparations]

- Recent alcohol consumption or recreational drug/narcotic use
 - Recent unaccustomed physical exertion
 - Occupational or environmental exposure to hepatotoxins
 - Other conditions which may cause liver diseases or which may cause abnormal test results
- Specialized Liver Laboratory Panel (see below)

14.4 Specialized Liver Panel

For patients who are being monitored frequently as a result of confirmed AST and/or ALT >3X ULN, additional central laboratory tests will be performed within 3 days of receipt of confirmatory results. These laboratory tests will study the possible causes of the increased ALT and/or AST and/or TB, and may include, but are not limited to, the following tests:
Hepatitis A IgM

- Hepatitis BsAg
- Hepatitis B Core Ab IgM
- Hepatitis C virus RNA
- Hepatitis C Ab
- Hepatitis E IgM
- Epstein-Barr Virus (EBV) IgM Ab
- Lactate Dehydrogenase (LDH)
- Gamma-glutamyl-transpeptidase (GGT)
- Carbohydrate deficient transferrin (CDT)
- Prothrombin time (PT/INR)
- Iron Panel - iron, ferritin, total iron binding capacity (TIBC)
- Immunology Panel including Antinuclear Antibody (ANA), Anti-Smooth Muscle Antibody (SMA) and Anti-Liver/Kidney Microsomal Antibody (Anti-LKM)
- Anti-tissue Transglutaminase Antibody

[figure not shown]
